Programming Note: Parameters will be Total Score, Motor Signs, Disability, Motor Complications, and Cognitive Status. Visits will be Baseline (Visit 2), Week 8 (Visit 10), and Week 24 (Visit 19). Add CISI-PD to abbreviations. Update footnote to read "1] The baseline value is the CISI-PD Score from Visit 2 or before." SOURCE: Listing 16.2.6.5. Update footnote to reflect Per Protocol Set.

Table 14.2.5.4
Mean Change from Baseline in CISI-PD Total Score by Study Visit and Treatment
Tabulation of Fitted Summary Statistics from ANCOVA
Per Protocol Set

Programming Note: Add CISI-PD to abbreviations. SOURCE: Listing 16.2.6.5. Update footnote to reflect Per Protocol Set.

Statistical Analysis Plan,
Sponsor: Alkermest, Inc.
Protocol Number ALK6021-201
PCN Number ALKA7951

Table 14.2.5.5
Summary of Change from Baseline in CISI-PD Scores by Treatment
Complete Set

(Same Shell as Table 14.2.1.1)

Programming Note: Parameters will be Total Score, Motor Signs, Disability, Motor Complications, and Cognitive Status. Visits will be Baseline (Visit 2), Week 8 (Visit 10), and Week 24 (Visit 19). Add CISI-PD to abbreviations. Update footnote to read T1] The baseline value is the CISI-PD Score from Visit 2 or before." SOURCE: Listing 16.2.6.5. Update footnote to reflect Complete Set.

Table 14.2.5.6
Mean Change from Baseline in CISI-PD Total Score by Study Visit and Treatment
Tabulation of Fitted Summary Statistics from ANCOVA
Complete Set

Programming Note: Add CISI-PD to abbreviations. SOURCE: Listing 16.2.6.5. Update footnote to reflect Complete Set.

Statistical Analysis Plan,
Sponsor Alkermes, Inc.
Protocol Number ALK6021-201
PCN Number ALKA7951

Table 14.2.6.1
Summary of Change from Baseline in PDQ-39 Scores by Treatment
Evaluable Set

(Same Shell as Table 14.2.1.1)
Programming Note: Parameters will be Total Score, Mobility, Activities of Daily Living, Emotional Well-Being, Stigma, Social Support, Cognitions, Communication, and Bodily Discomfort. Visits will be Baseline (Visit 2), Week 4 (Visit 9), Week 8 (Visit 10), Week 8 (Visit 18), and Week 24 (Visit 19). Add PDQ-39 to abbreviations. Update footnote to read "Note: PDQ-39 is scored on a scale of 0-100 with lower scores indicating better health and high scores indicating more severe symptoms. [1] The baseline value is the PDQ-39 Score from Visit 2 or before." SOURCE: Listing 16.2.6.6.

Table 14.2.6.2
Mean Change from Baseline in PDQ-39 Total Score by Study Visit and Treatment
Tabulation of Fitted Summary Statistics from ANCOVA
Evaluable Set

(Same Shell as Table 14.2.1.2)
Programming Note: Add PDQ-39 to abbreviations. SOURCE: Listing 16.2.6.6.

Table 14.2.6.3
Summary of Change from Baseline in PDQ-39 Scores by Treatment
Per Protocol Set

(Same Shell as Table 14.2.1.1)
Programming Note: Parameters will be Total Score, Mobility, Activities of Daily Living, Emotional Well-Being, Stigma, Social Support, Cognitions, Communication, and Bodily Discomfort. Visits will be Baseline (Visit 2), Week 4 (Visit 9), Week 8 (Visit 10), Week 8 (Visit 18), and Week 24 (Visit 19). Add PDQ-39 to abbreviations. Update footnote to read "Note: PDQ-39 is scored on a scale of 0-100 with lower scores indicating better health and high scores indicating more severe symptoms. [1] The baseline value is the PDQ-39 Score from Visit 2 or before." SOURCE: Listing 16.2.6.6. Update footnote to reflect Per Protocol Set.

Table 14.2.6.4
Mean Change from Baseline in PDQ-39 Total Score by Study Visit and Treatment
Tabulation of Fitted Summary Statistics from ANCOVA
Per Protocol Set

(Same Shell as Table 14.2.1.2)
Programming Note: Add PDQ-39 to abbreviations. SOURCE: Listing 16.2.6.6. Update footnote to reflect Per Protocol Set.

Statistical Analysis Plan,
Sponsor Alkahest, Inc.
Protocol Number ALK6021-201
PCN Number ALKA7951

Table 14.2.6.5
Summary of Change from Baseline in PDQ-39 Scores by Treatment Complete Set

(Same Shell as Table 14.2.1.1)

Programming Note: : Parameters will be Total Score, Mobility, Activities of Daily Living, Emotional Well-Being, Stigma, Social Support, Cognitions, Communication, and Bodily Discomfort. Visits will be Baseline (Visit 2), Week 4 (Visit 9), Week 8 (Visit 10), Week 20 (Visit 18), and Week 24 (Visit 19). Add PDQ-39 to abbreviations. Update footnote to read "Note: PDQ-39 is scored on a scale of 0-100 with lower scores indicating better health and high scores indicating more severe symptoms. [1] The baseline value is the PDQ-39 Score from Visit 2 or before." SOURCE: Listing 16.2.6.6. Update footnote to reflect Complete Set.

Table 14.2.6.6

Mean Change from Baseline in PDQ-39 Total Score by Study Visit and Treatment Tabulation of Fitted Summary Statistics from ANCOVA Complete Set

(Same Shell as Table 14.2.1.2)

Programming Note: Add PDQ-39 to abbreviations.SOURCE: Listing 16.2.6.6. Update footnote to reflect Complete Set.

Statistical Analysis Plan,
Sponsor Alkermes, Inc
Protocol Number ALK6021-201
PCN Number ALKA7951

Table 14.2.7.1
Summary of GDS-15 Categories by Study Visit and Treatment
Evaluable Set

Study Visit Category	Placebo (N=XX)	GRF6021 (N=XX)
Baseline [1]		
0-4 No depression	XX (XX.X%)	XX (XX.X%)
5-10 Mild depression	XX (XX.X%)	XX (XX.X%)
11 + Severe depression	XX (XX.X%)	XX (XX.X%)
Week 8 (Visit 10)		
0-4 No depression	XX (XX.X%)	XX (XX.X%)
5-10 Mild depression	XX (XX.X%)	XX (XX.X%)
11 + Severe depression	XX (XX.X%)	XX (XX.X%)
Week 20 (Visit 18)		
0-4 No depression	XX (XX.X%)	XX (XX.X%)
5-10 Mild depression	XX (XX.X%)	XX (XX.X%)
11 + Severe depression	XX (XX.X%)	XX (XX.X%)

Abbreviation: GDS-15 = Geriatric Depression Scale-15.
Note: Percentages are n/Number of subjects in the Evaluable Set*100. Subjects are summarized by randomized treatment.
[1] The baseline value is the SDS-15 assessment from Visit 2 or before.
SOURCE: Listing 16.2.6.7

Statistical Analysis Plan,
Sponsor Alkermes, Inc.
Protocol Number ALK6021-201
PCN Number ALKA7951

Table 14.2.7.2
Summary of Change from Baseline in GDS-15 Total Score by Treatment
Evaluable Set

(Same Shell as Table 14.2.1.1)

Programming Note: Parameter will be Total Score Visits will be Baseline (Visit 2), Week 8 (Visit 10), and Week 20 (Visit 18). Add GDS-15 to abbreviations. Update footnote to read "Note: Each item is recorded as yes or no which is assigned a numeric value of 1 or 0, respectively. The final score is the tally of the number of depressive answers with the following scores indicating depression: 0-4 No depression, 5-10 Suggestive of a mild depression, 11 + Suggestive of severe depression. [1] The baseline value is the PDQ-39 Score from Visit 2 or before." SOURCE: Listing 16.2.6.7.

Table 14.2.7.3
Mean Change from Baseline in GDS-15 Total Score by Study Visit and Treatment
Tabulation of Fitted Summary Statistics from ANCOVA
Evaluable Set

(Same Shell as Table 14.2.1.2)

Programming Note: Add GDS-15 to abbreviations. SOURCE: Listing 16.2.6.7.

Table 14.2.7.4
Summary of GDS-15 Categories by Study Visit and Treatment
Per Protocol Set

Same Shell as Table 14.2.7.1

Programming Note: Add GDS-15 to abbreviations. Update footnote to reflect Per Protocol Set. SOURCE: Listing 16.2.6.7.

Table 14.2.7.5
Summary of Change from Baseline in GDS-15 Total Score by Treatment
Per Protocol Set

Same Shell as Table 14.2.1.1

Programming Note: Parameter will be Total Score Visits will be Baseline (Visit 2), Week 8 (Visit 10), and Week 20 (Visit 18). Add GDS-15 to abbreviations. Update footnote to read "Note: Each item is recorded as yes or no which is assigned a numeric value of 1 or 0, respectively. The final score is the tally of the number of depressive answers with the following scores indicating depression: 0-4 No depression, 5-10 Suggestive of a mild depression, 11 + Suggestive of severe depression. [1] The baseline value is the PDQ-39 Score from Visit 2 or before." SOURCE: Listing 16.2.6.7. Update footnote to reflect Per Protocol Set.

Table 14.2.7.6
Mean Change from Baseline in GDS-15 Total Score by Study Visit and Treatment
Tabulation of Fitted Summary Statistics from ANCOVA
Per Protocol Set

(Same Shell as Table 14.2.1.2)
Programming Note: Add GDS-15 to abbreviations. SOURCE: Listing 16.2.6.7.

Table 14.2.7.7
Summary of GDS-15 Categories by Study Visit and Treatment
Complete Set

Same Shell as Table 14.2.7.1
Programming Note: Add GDS-15 to abbreviations. Update footnote to reflect Per Protocol Set. SOURCE: Listing 16.2.6.7.

Table 14.2.7.8
Summary of Change from Baseline in GDS-15 Total Score by Treatment
Complete Set

Same Shell as Table 14.2.1.1
Programming Note: Parameter will be Total Score Visits will be Baseline (Visit 2), Week 8 (Visit 10), and Week 20 (Visit 18). Add GDS-15 to abbreviations. Update footnote to read "Note: Each item is recorded as yes or no which is assigned a numeric value of 1 or 0, respectively. The final score is the tally of the number of depressive answers with the following scores indicating depression: 0-4 No depression, 5-10 Suggestive of a mild depression, 11 + Suggestive of severe depression. [1] The baseline value is the PDQ-39 Score from Visit 2 or before." SOURCE: Listing 16.2.6.7. Update footnote to reflect Per Protocol Set.

Table 14.2.7.9
Mean Change from Baseline in GDS-15 Total Score by Study Visit and Treatment
Tabulation of Fitted Summary Statistics from ANCOVA
Complete Set

(Same Shell as Table 14.2.1.2)
Programming Note: Add GDS-15 to abbreviations. SOURCE: Listing 16.2.6.7.

Statistical Analysis Plan,
Sponsor Alkermes, Inc.
Protocol Number ALK6021-201
PCN Number ALKA7951

Table 14.2.8.1
Summary of Change from Baseline in dCDT Score by Treatment
Evaluable Set

(Same Shell as Table 14.2.1.1)
Programming Note: Visits will be Baseline (Visit 2), Week 1 (Visit 8), Week 8 (Visit 10), Week 13 (Visit 16), and Week 20 (Visit 18). Add dCDT to abbreviations. Update footnote to read "[1] The baseline value is the dCDT Score from Visit 2 or before." SOURCE: Listing 16.2.6.8.

Table 14.2.8.2
Mean Change from Baseline in dCDT Score by Study Visit and Treatment
Tabulation of Fitted Summary Statistics from ANCOVA
Evaluable Set

(Same Shell as Table 14.2.1.2)
Programming Note: Add dCDT to abbreviations. SOURCE: Listing 16.2.6.8.

Table 14.2.8.3
Summary of Change from Baseline in dCDT Score by Treatment
Per Protocol Set

(Same Shell as Table 14.2.1.1)
Programming Note: Visits will be Baseline (Visit 2), Week 1 (Visit 8), Week 8 (Visit 10), Week 13 (Visit 16), and Week 20 (Visit 18). Add dCDT to abbreviations. Update footnote to read "[1] The baseline value is the dCDT Score from Visit 2 or before." SOURCE: Listing 16.2.6.8.

Table 14.2.8.4
Mean Change from Baseline in dCDT Score by Study Visit and Treatment
Tabulation of Fitted Summary Statistics from ANCOVA
Per Protocol Set

(Same Shell as Table 14.2.1.2)
Programming Note: Parameter will be dCDT total score. Add dCDT to abbreviations. SOURCE: Listing 16.2.6.8.

Table 14.2.8.5
Summary of Change from Baseline in dCDT Score by Treatment
Complete Set

Programming Note: Visits will be Baseline (Visit 2), Week 1 (Visit 8), Week 8 (Visit 10), Week 13 (Visit 16), and Week 20 (Visit 18). Add dCDT to abbreviations. Update footnote to read "[1] The baseline value is the dCDT Score from Visit 2 or before." SOURCE: Listing 16.2.6.8.

Table 14.2.8.6
Mean Change from Baseline in dCDT Score by Study Visit and Treatment
Tabulation of Fitted Summary Statistics from ANCOVA
Complete Set

Programming Note: Parameter will be dCDT total score. Add dCDT to abbreviations. SOURCE: Listing 16.2.6.8.

Table 14.2.8.7
dCDT Classification by Study Visit and Treatment
Evaluable Set

Study Visit Statistic	Placebo (N=XX)	GRF6021 (N=XX)
Baseline [1]		
Within normal limits	XX (XX.X%)	XX (XX.X%)
Indeterminate	XX (XX.X%)	XX (XX.X%)
Outside normal limits	XX (XX.X%)	XX (XX.X%)
Unanalyzable	XX (XX.X%)	XX (XX.X%)
Week 1 (Visit 8)		
Within normal limits	XX (XX.X%)	XX (XX.X%)
Indeterminate	XX (XX.X%)	XX (XX.X%)
Outside normal limits	XX (XX.X%)	XX (XX.X%)
Unanalyzable	XX (XX.X%)	XX (XX.X%)
Week 8 (Visit 10)		
Within normal limits	XX (XX.X%)	XX (XX.X%)
Indeterminate	XX (XX.X%)	XX (XX.X%)
Outside normal limits	XX (XX.X%)	XX (XX.X%)
Unanalyzable	XX (XX.X%)	XX (XX.X%)

Continue for other visits.

Abbreviation: dCDT = Digital clock drawing test.
Note: Percentages are n/Number of subjects in the Evaluable Set*100. Subjects are summarized by randomized treatment.
[1] The baseline value is the dCDT Score from Visit 2 or before.
SOURCE: Listing 16.2.6.8

Table 14.2.8.8
dCDT Classification by Study Visit and Treatment Treatment
Per Protocol Set

(Same shell as Table 14.2.8.7)
Programming Note: Update footnote to reflect Per Protocol Set

Table 14.2.8.9
dCDT Classification by Study Visit and Treatment Treatment
Complete Set

(Same shell as Table 14.2.8.7)
Programming Note: Update footnote to reflect Complete Set

Statistical Analysis Plan,
 Sponsor: Alkermest, Inc.
 Protocol Number ALK6021-201
 PCN Number ALKA7951

Table 14.2.9.1
 Screening Safety MRI Results by Study Visit and Treatment
 Evaluable Set

Visit: Screening	Placebo (N=XX)	GRF6021 (N=XX)
Test Category		
Presence of MRI Abnormalities		
Yes	XX (XX.X%)	XX (XX.X%)
No	XX (XX.X%)	XX (XX.X%)
Nonevaluable	XX (XX.X%)	XX (XX.X%)
Abnormalities Present		
Cerebral edema	XX (XX.X%)	XX (XX.X%)
Abnormality Primary Location		
Right frontal	XX (XX.X%)	XX (XX.X%)
Right temporal, non hippocampal	XX (XX.X%)	XX (XX.X%)
Right parietal	XX (XX.X%)	XX (XX.X%)
Right occipital	XX (XX.X%)	XX (XX.X%)
...		
Abnormality Status		
Present	XX (XX.X%)	XX (XX.X%)
Presence is questionable	XX (XX.X%)	XX (XX.X%)
Abnormality Sequence		
3DT1	XX (XX.X%)	XX (XX.X%)
FLAIR	XX (XX.X%)	XX (XX.X%)
T2*	XX (XX.X%)	XX (XX.X%)
T2	XX (XX.X%)	XX (XX.X%)
DWI	XX (XX.X%)	XX (XX.X%)
Other	XX (XX.X%)	XX (XX.X%)
Microhemorrhage		
Abnormality Primary Location		
Right frontal	XX (XX.X%)	XX (XX.X%)
...		
Abnormality Status		
Present	XX (XX.X%)	XX (XX.X%)
Presence is questionable	XX (XX.X%)	XX (XX.X%)
Abnormality Sequence		
3DT1	XX (XX.X%)	XX (XX.X%)
...		

Abbreviations: MRI = magnetic resonance imaging; PD = Parkinson's Disease.
 Note: Percentages are n/Number of subjects in the Evaluable Set*100. Subjects are summarized by randomized treatment.
 SOURCE: Listing 16.2.6.10

Table 14.2.9.1 (cont.)
Screening MRI Results by Study Visit and Treatment
Evaluable Set

Visit: Screening	Placebo (N=XX)	GRF6021 (N=XX)
Test Category		
White matter disease present		
No lesions (including symmetrical, well-defined caps or bands)	XX (XX.X%)	XX (XX.X%)
Focal lesions	XX (XX.X%)	XX (XX.X%)
Beginning confluence of lesions	XX (XX.X%)	XX (XX.X%)
Diffuse involvement of entire region, with or without involvement of U-fibers	XX (XX.X%)	XX (XX.X%)
Non Evaluable	XX (XX.X%)	XX (XX.X%)
Potential alternative diagnosis to PD		
Yes	XX (XX.X%)	XX (XX.X%)
No	XX (XX.X%)	XX (XX.X%)
Nonevaluable	XX (XX.X%)	XX (XX.X%)

Abbreviations: MRI = magnetic resonance imaging; PD = Parkinson's Disease.
Note: Percentages are n/Number of subjects in the Evaluable Set*100. Subjects are summarized by randomized treatment.
SOURCE: Listing 16.2.6.10

Programming Note: Continue for Visit 16 for subjects who consented to additional MRI. Only categories with at least 1 subject should be presented for the following tests:
Abnormalities Present, Abnormality Primary Location, and Abnormality Sequence.
Potential abnormalities are: Cerebral edema, Microhemorrhage, Microhemorrhage (>1cm); Superficial siderosis; Subdural hemorrhage/hematoma; Epidural haemorrhage; Subarachnoid haemorrhage; Intraventricular haemorrhage; Stroke involving a major vascular territory; Lacunar infarct (10-15 mm); Cortical infarct; Other infarct; Cerebral contusion; Encephalomalacia; Aneurysm or Vascular malformation; Hydrocephalus; Infective lesion; Meningioma ≥ 1 cm in diameter; Meningioma < 1 cm in diameter; Arachnoid cyst ≥ 1 cm in diameter; Arachnoid cyst < 1 cm in diameter; Other space occupying lesion or Brain tumor; Other.
Potential Abnormality primary locations are: Right frontal; Right temporal, non hippocampal; Right parietal; Right occipital; Right chippocampus; Right cerebellum; Mid-brain; Medulla; Leptomeninges; Left frontal; Left temporal, non hippocampal; Left parietal; Left occipital; Left chippocampus; Left cerebellum; Hydrocephalus; Pons; Deep grey matter structures; Ventricular system; All brain; Other.
Potential abnormality sequences are: DTI; FLAIR; T2*; T2; DWI; Other

Statistical Analysis Plan,
Sponsor: Alkermes, Inc.
Protocol Number ALK6021-201
PCN Number: ALKA7951

Table 14.2.9.2
Screening Safety MRI Results by Study Visit and Treatment
Per Protocol Set

(Same shell as Table 14.2.9.1)

Table 14.2.9.3
Volumetric MRI Results by Study Visit and Treatment
Evaluable Set

Location Laterality Statistic	Placebo (N=XX)	GRF6021 (N=XX)
Whole Brain		
Bilateral		
n	XX	XX
Mean (SD)	XX.X (XX.XX)	XX.X (XX.XX)
Median	XX.X	XX.X
Min, Max	XX, XX	XX, XX
Lateral Ventricles		
Bilateral		
n	XX	XX
Mean (SD)	XX.X (XX.XX)	XX.X (XX.XX)
Median	XX.X	XX.X
Min, Max	XX, XX	XX, XX
Intracranial		
Bilateral		
n	XX	XX
Mean (SD)	XX.X (XX.XX)	XX.X (XX.XX)
Median	XX.X	XX.X
Min, Max	XX, XX	XX, XX
Cortical		
Left		
n	XX	XX
Mean (SD)	XX.X (XX.XX)	XX.X (XX.XX)
Median	XX.X	XX.X
Min, Max	XX, XX	XX, XX
Right		
n	XX	XX

Abbreviations: MRI = magnetic resonance imaging.

Note: Percentages are n/Number of subjects in the Evaluable Set*100. Subjects are summarized by randomized treatment.

SOURCE: Listing 16.2.6.11

Programming note: For Visit: Screening, Additional locations for Test: Volume (mm³) will be Hippocampus (left, right, bilateral). Repeat table for Test: Cerebral Cortex Average Thickness (mm) and Cerebral Cortex Thickness Average Change (mm). Locations will be Cortical (left, right, bilateral), Mayo (bilateral), Prefrontal Lobe (left, right, bilateral), Whole Temporal Lobe (left, right, bilateral), Superior Temporal Lobe (left, right, bilateral), Medial Temporal Lobe (left, right, bilateral), Lateral Parietal Lobe (left, right, bilateral), Inferior Parietal Lobe (left, right, bilateral), Precuneus (left, right, bilateral), Isthmuscingulate (left, right, bilateral), Entorhinal Cortex (left, right, bilateral). Repeat table for Test: Atrophy (mm²). Locations will be the same as Test: Volume with the exception of Intracranial.
Repeat table for Visit: Week 13 (Visit 16).

Statistical Analysis Plan,
Sponsor: Alkermest, Inc.
Protocol Number ALK6021-201
PCN Number ALKA7951

Table 14.2.9.4
ASL MRI Results by Study Visit and Treatment
Evaluable Set

Visit: Screening	Location	Placebo (N=XX)	GRF6021 (N=XX)
	Frontal Lobe		
	Left		
	n	XX	XX
	Mean (SD)	XX.X (XX.XX)	XX.X (XX.XX)
	Median	XX.X	XX.X
	Min, Max	XX, XX	XX, XX
	Right		
	n	XX	XX
	Mean (SD)	XX.X (XX.XX)	XX.X (XX.XX)
	Median	XX.X	XX.X
	Min, Max	XX, XX	XX, XX
	Bilateral		
	n	XX	XX
	Mean (SD)	XX.X (XX.XX)	XX.X (XX.XX)
	Median	XX.X	XX.X
	Min, Max	XX, XX	XX, XX
	Cingulate Cortex		
	Left		
	n	XX	XX
	Mean (SD)	XX.X (XX.XX)	XX.X (XX.XX)
	Median	XX.X	XX.X
	Min, Max	XX, XX	XX, XX

Abbreviations: ASL = arterial-spin labeling; MRI = magnetic resonance imaging.
Note: Percentages are n/Number of subjects in the Evaluable Set*100. Subjects are summarized by randomized treatment. Cerebral blood flow measurements are presented in mL/100g/min.
SOURCE: Listing 16.2.6.12

Programming note: For Visit: Screening, Additional locations will be Frontal lobe, Cingulate cortex, Parietal lobe, Temporal lobe, Occipital lobe, Striatum, Cerebellum, Thalamus, Pallidum, Substantia nigra, Hippocampus. Left, Right, and Bilateral sides will be present for all.
Repeat table for Visit: Week 13 (Visit 16).

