Each infusion will have a duration of approximately [REDACTED] with a maximum of [REDACTED]. The infusion of active and placebo agents will be identical to maintain blinding. The following measures will be taken to ensure adequate allocation concealment during infusions: blinding of subjects, trial partners, study coordinators, physicians, and cognitive/motor test administrators to treatment allocation; use of blinded Outcomes Assessors and unblinded Infusion Nurses; and measures to block view of the infusion setup to avoid unblinding.

All subjects will undergo a screening visit, including a magnetic resonance imaging (MRI) scan, baseline visit, two treatment periods, follow-up visits, and an end-of-study/early-termination visit. During each 5-day treatment period, administration of GRF6021/placebo can occur in an inpatient/hospital setting or in outpatient infusion centers or equivalent facilities with appropriate medical personnel. All infusions must be performed by adequately trained personnel under the supervision of the investigator. Safety and tolerability assessments will occur at every visit. Neurocognitive and motor assessments will be performed at baseline and at periodic visits following dosing. Subjects who provide explicit consent to undergo a second, optional MRI scan will have an additional MRI scan at Visit 16 to assess for changes from screening.

Objectives: The primary objective of the study is to assess the safety and tolerability of an infusion dosing regimen of GRF6021 in subjects with PD and cognitive impairment. As a secondary objective, the study will assess the potential effects of GRF6021 on cognition and motor function as well as changes from baseline in clinical laboratory parameters, vital signs, body weight, and the Sheehan-Suicidality Tracking Scale (S-STSS). The exploratory objectives include serial compositional analysis of plasma to identify

specific biomarkers associated with cognitive and motor function and/or indicators of disease progression, and changes on MRI (in consenting subjects).

Endpoints:

Primary Endpoint:

- Incidence of treatment-emergent adverse events (TEAEs) and serious adverse events (SAEs) identified by the Medical Dictionary for Regulatory Activities (MedDRA) preferred term (PT) and grouped by MedDRA System Organ Class (SOC).

Secondary Efficacy Endpoints:

- Change from baseline in the Montreal Cognitive Assessment (MoCA).

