 16. Current, active liver disease or known hepatic or biliary abnormalities.
 17. Uncontrolled diabetes defined as hemoglobin A1c (HbA1c) > 7.5%.
 18. Clinically significant abnormalities in complete blood count, complete metabolic panel, serum albumin, serum lipids, coagulation, or levels of thiamine, pyridoxine, cobalamin, and thyroid stimulating hormone.
 19. Positive urine drug screen. The presence of opioids, benzodiazepines, and/or amphetamines in the urine drug screen may be allowed if these are prescribed and the dose stable for at least 8 weeks prior to screening.
 20. Hemoglobin < 10 g/dL in women and < 11 g/dL in men.
 21. Urine protein-to-creatinine ratio (UPCR) of > 1.5 grams of protein per gram of creatinine.
 22. Inadequate venous access to allow IV drug delivery or multiple blood draws.
 23. Concurrent participation in any other therapeutic treatment trial. If there was prior clinical trial participation, subject must have discontinued investigational agents for at least 30 days for small molecules, and 1 year for active or passive immunotherapies prior to screening.
 24. If on deep brain stimulation (DBS), DBS surgery within 12 months of screening and/or a change in DBS settings within 12 weeks of screening. DBS settings must not be changed at any point during the subject's participation in the trial.
 25. Presence of a pacemaker or any other implant that would be an MRI contraindication, including DBS if not MRI compatible.
 26. More than 2 lacunar strokes or other clinically-relevant imaging abnormality on screening MRI.
 27. Any other condition and/or situation that the investigator believes may interfere with the safety of the subject, study conduct, or interpretation of study data.

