8.3.2. Magnetic Resonance Imaging (MRI)

MRI will be used to evaluate subjects' eligibility for inclusion in the study at screening. Structural images will be interpreted by a central reader at screening and any exclusionary findings will be reported. Where available, functional imaging will also be acquired to assess for functional connectivity as measured by tf-fMRI and cerebral blood flow as measured by ASL MRI. In consenting subjects, an additional MRI at Visit 16 will assess for changes in brain atrophy as measured by MRI, functional connectivity as measured by tf-fMRI, and cerebral blood flow as measured ASL MRI. During the MRI, the subject will be asked to lie on a narrow bed in a large tunnel while images are captured by the MRI machine. Participation in the screening MRI is required, while participation in the additional MRI at Visit 16 is optional and not required for inclusion in the study.

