8.3.2.1. Safety MRI

The number and percentage of subjects with presence of screening safety MRI abnormalities along with the type of abnormality and primary location of abnormality reported will be presented by treatment group. Additionally, abnormality sequence, abnormality status, and presence of white matter disease will be tabulated by treatment group. The number and percentage of subjects whose screening safety MRI findings suggest there is a potential alternative diagnosis to PD will also be presented.

Screening safety MRI results will be listed.

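### The Visit 16 safety MRI rows show prevalence in an optional subset, and no planned summary table pairs a subject's two abnormality reads, so new or worsened lesions by arm cannot be taken from the tables

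*SAP*

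**What the plan says.** SAP 8.3.2.1 describes the safety MRI at screening only: "The number and percentage of subjects with presence of screening safety MRI abnormalities along with the type of abnormality" is to be presented by treatment group, with location, sequence, status and white-matter disease. It does not mention Visit 16.

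Visit 16 enters through the programming note under Table 14.2.9.1: "Continue for Visit 16 for subjects who consented to additional MRI". The note carries the screening rows forward: presence of any abnormality, each type, location and sequence within type, status, and white-matter category. The status row has two values, present and "Presence is questionable". Neither says new, worsened or pre-existing. Table 14.2.9.2 reuses the shell for the Per Protocol Set.

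Three other provisions bear on this:

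- **Entry.** Protocol exclusion criterion 26 removes subjects with "More than 2 lacunar strokes or other clinically-relevant imaging abnormality on screening MRI". Up to two lacunar strokes, and findings not judged clinically relevant, are therefore allowed at screening.
- **Who is rescanned.** SAP 8.3.2 states that "participation in the additional MRI at Visit 16 is optional".
- **Denominator.** The shell footnote reads "Percentages are n/Number of subjects in the Evaluable Set*100", whereas SAP 4.1 bases by-visit displays on subjects with data at that visit.

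Elsewhere the SAP does plan within-subject comparison: shift tables for laboratory results (SAP 9.2), and follow-up change in atrophy and cortical thickness (SAP 8.3.2.2, Table 14.2.9.3).

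**The concern.** Nothing in the note or the row labels limits the Visit 16 rows to new findings, so a lesion already seen at screening would be counted again after treatment. The documents do not say this outright, but it follows from repeating unchanged categories. A further lesion in a subject who already has one leaves the overall presence row unchanged. The two blocks also cannot be subtracted, because screening covers all Evaluable subjects and Visit 16 only those rescanned.

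At stake is whether a table titled as safety MRI, in a trial whose primary objective is safety, can show what changed after treatment. As planned, it mixes old findings with any new ones and leaves the reader to separate them.

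**Working it through.** The plan states no figure for this display, so there is none to reproduce. The check has three steps. Every lesion and rescan rate in it is an assumption.

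**1. Is there a paired display of abnormality reads?**

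| Data | Within-subject comparison in a summary table |
|---|---|
| Laboratory results | Yes, shift tables (SAP 9.2) |
| Atrophy and cortical thickness | Yes, follow-up change (Table 14.2.9.3) |
| Safety MRI abnormalities | None; by-visit counts only (Tables 14.2.9.1 and 14.2.9.2) |

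**2. What can be recovered from the by-visit counts?** The protocol assumes 25% dropout: 90 × (1 − 0.25) = 67.5, its approximately 68 evaluable subjects. At 2:1 this is about 45 on GRF6021 and 23 on placebo. Let N be the evaluable subjects in an arm, m those rescanned, a those abnormal at screening and b those abnormal at Visit 16. Assume lesions persist. Of the b subjects, k were already abnormal, where k lies between max(0, a − (N − m)) and min(a, b). Newly abnormal subjects number b − k. Assume 10% or 30% abnormal at both visits, and about 50% or 80% rescanned.

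| Arm | N | m | a | b | k | Newly abnormal |
|---|---|---|---|---|---|---|
| GRF6021, 30% | 45 | 22 | 14 | 7 | 0 to 7 | 0 to 7 |
| GRF6021, 30% | 45 | 36 | 14 | 11 | 5 to 11 | 0 to 6 |
| GRF6021, 10% | 45 | 22 | 4 | 2 | 0 to 2 | 0 to 2 |
| GRF6021, 10% | 45 | 36 | 4 | 4 | 0 to 4 | 0 to 4 |
| Placebo, 30% | 23 | 12 | 7 | 4 | 0 to 4 | 0 to 4 |
| Placebo, 30% | 23 | 18 | 7 | 5 | 2 to 5 | 0 to 3 |

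The same counts fit no new cases, or in the half-rescanned rows every Visit 16 case being new. If everyone were rescanned and lesions persisted, the net difference would equal the newly abnormal subjects, so the optional subset is what removes the information from this row. The denominator matters as well: 7/45 = 15.6%, but 7/22 = 31.8%.

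**3. How precise would a paired count be?** Suppose 4 of 45 GRF6021 subjects and 0 of 23 placebo subjects have a new lesion, with everyone rescanned. The difference is 8.9 points. The Wilson intervals are 3.5% to 20.7% and 0% to 14.3%. Combining them by Newcombe's method:

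- lower limit: 8.9 − √((8.9 − 3.5)² + 14.3²) = −6.4
- upper limit: 8.9 + (20.7 − 8.9) = 20.7

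With 2/22 versus 0/11 the difference is 9.1 points, 95% CI −17.6 to 27.8.

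**The case against.** Several stronger readings are tempting, and the documents do not support them.

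- **A reader might infer that no table compares the two scans at all.** Table 14.2.9.3 does, for atrophy and cortical thickness. The gap is confined to the abnormality reads.
- **A reader might infer that new lesions by arm are lost.** Listing 16.2.6.10 gives treatment, visit, type, slice, location, status and white-matter category for each subject, and listings are sorted by treatment. With about 68 evaluable subjects, pairing by hand is feasible. Under Protocol 8.1.1, a new or worse finding judged clinically significant is an AE and reaches the TEAE tables by arm.
- **A reader might take the Protocol Summary's statement that consenting subjects "will have an additional MRI scan at Visit 16 to assess for changes from screening" as a promise to look for new lesions.** Protocol 4.1 and 7.2.2.2 specify the changes as atrophy, cortical thinning, functional connectivity and cerebral blood flow. MRI change is an exploratory endpoint.
- **A reader might assume that most Visit 16 findings are old.** The documents give no rates, and clinically relevant abnormalities are excluded at entry.
- **A reader might expect counting new lesions to give a sharp comparison.** A simple standard error looks small if the placebo rate is set at exactly zero, because placebo then adds no variance. Step 3 shows the real width.

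It is also true that rows by type would show some new lesions, such as a first microhaemorrhage in a subject with an old lacune. Consent to the optional scan is taken at screening, so the arms within the subset should be comparable apart from dropout and missed scans. Prevalence dilutes a difference; it does not create one.

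These points narrow the finding and lower its priority. They do not supply a planned summary of new or worsened abnormalities. Pairing by hand is not a prespecified result, and a silent finding not judged clinically significant need not become an AE.

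**Conclusion.** The point holds for the planned summary tables. The Visit 16 block of Tables 14.2.9.1 and 14.2.9.2 is prevalence in an optional subset, and no summary table pairs the two abnormality reads. New or worsened lesions by arm cannot be taken from those tables.

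The size of the dilution cannot be stated. The ranges in step 2 rest on assumed abnormality and rescan rates, on lesions persisting, and on the overall presence row alone. The primary endpoint, the secondary endpoints and the volumetric MRI analysis are unaffected. The matter is minor, but worth correcting because the data are already captured.

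**What to change.** For subjects with evaluable safety reads at both screening and Visit 16, add to Tables 14.2.9.1 and 14.2.9.2, by arm:

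1. n (%) with at least one new abnormality, meaning one whose type, location and slice has no match at screening. Using slice as well as location lets a second lesion of the same type in the same region count. State before unblinding how close two slice numbers must be to match. Show reads of "Presence is questionable" at either visit separately and do not count them as new, so that a change in reader certainty is not reported as a lesion.
2. n (%) with a worse white-matter category than at screening.

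Use the number of paired reads as denominator, with Wilson intervals as in SAP 9.1. Label the existing Visit 16 rows as prevalence, and add a sentence on Visit 16 to SAP 8.3.2.1.

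The cost is SAP wording and programming. The fields are already in Listing 16.2.6.10, and no study procedure changes. The downside is small denominators, because the second scan is optional, so the block should stay descriptive.
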